2.5.5 Subgroup analysis

For primary endpoint and its components, subgroup analyses will be performed based on the pre-defined subgroups in [section 2.2.1](#) for patients in FAS only.

Displays of treatment effects by subgroup categories (defined as marginal groupings) will be provided for descriptive purposes.

The estimated hazard ratio, and 2-sided 95% confidence interval, will be provided for each individual subgroup using a Cox's proportional hazards model stratified by STEMI/NSTEMI with treatment, region and PCI use at baseline as fixed effects factor in the model, with the exception for type of MI (STEMI/ NSTEMI) subgroup for which the analysis will not be stratified by STEMI/ NSTEMI.

For subgroups other than type of MI (STEMI vs. NSTEMI), the p-value associated with the test of treatment-by-subgroup interaction effect will be calculated from a Cox's proportional hazards model, stratified by STEMI/NSTEMI, including treatment, PCI use at baseline, region, subgroup, and treatment-by-subgroup as fixed-effect factors. For STEMI vs. NSTEMI, p-value for interaction term will be provided from a similar model but STEMI/NSTEMI only included as a fixed effect factor and not a stratifying factor.

Since no adjustment for multiple comparisons will be made, findings should be interpreted with caution. Additionally, the frequency and percentage of patients reaching primary composite endpoint will be presented by treatment group for each of the subgroups listed in [Section 2.2.1](#).

2.6 Analysis of secondary efficacy objective(s)

The Full Analysis Set (FAS) will be used for all secondary analyses.

The general strategies for the main, sensitivity, and subgroup analyses of the secondary efficacy endpoints will be similar to those of the primary efficacy endpoint (see [Section 2.5](#)).

In the event that the study is stopped early for efficacy at the second interim analysis, or the study is terminated early by the sponsor due to prolonged COVID-19 impact, the main and subgroup analyses for the secondary endpoints described below (Section 2.6.2 and 2.6.6) will be performed using the same analysis cut-off date as the second interim analysis to include data prior to 01-Mar-2020.

If the study is not stopped at the second interim analysis and continues to the end, the main and subgroup analyses for the secondary endpoints described in this section will be performed as planned using all data accrued up to the end-of-study analysis cut-off (31-Dec-2020).

See Section 2.6.5 for sensitivity analyses added for the COVID-19 impact.

2.6.1 Secondary endpoints

The secondary variables are as follows-

- (1) Time from randomization to first occurrence of a confirmed composite of CV death or HF hospitalization
- (2) Time from randomization to first occurrence of a confirmed composite of HF hospitalization or outpatient HF
- (3) Time from randomization to first occurrence of a confirmed composite of CV death, non-fatal spontaneous MI or non-fatal stroke
 - *Non-fatal spontaneous MI is defined as either Type 1 or Type 2 MI confirmed by the independent Clinical Event Committee*
- (4) The cumulative number of composite events, including hospitalizations due to HF, hospitalizations due to non-fatal spontaneous MI, hospitalizations due to non-fatal stroke and CV death.
- (5) Time from randomization to all-cause mortality

Censoring of secondary endpoints

For time-to-first event endpoints, the general rules of the censoring methods in Section 2.5.3 will be followed.

For a time-to-recurrent event endpoint, the censoring date is defined as one of the following (whichever occurred first):

- Date when the patient withdrew informed consent
- Date of the patient's last visit (including telephone visit)
- Date of death
- Analysis cut-off date¹

¹ Analysis cut-off date will be 29-Feb-2020 for analyses using pre-COVID impact data prior to 1-Mar-2020.

The event generating process for the secondary endpoints will be censored following the mechanism below-

- Endpoints (1), (2) and (3) will be censored following a similar censoring mechanism followed for a non-fatal endpoint ([Section 2.5.3](#)).
- Event generating process for endpoint (4) will be censored following the censoring mechanism for a recurrent time-to-event endpoint as summarized above in this section.
- Endpoint (5) will be censored following the fatal endpoint censoring method (Section 2.5.3). For all-cause death, this means censoring at the earlier of
 - date when the patient withdrew informed consent
 - Patient's last known alive date

- Analysis cut-off date¹

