6.4 Efficacy

6.4.1 Efficacy assessment 1

The primary efficacy endpoint is defined as the time to the first confirmed occurrence of CV death, heart failure hospitalization* or outpatient heart failure**.

* *Heart failure hospitalization also includes the development of new symptomatic heart failure during an ongoing hospitalization including the index AMI hospitalization.*

** *Outpatient heart failure is defined as:*

- An urgent/unscheduled visit to an ED, acute/urgent care facility or outpatient clinic or a non-urgent office/practice or study visit for a primary diagnosis of HF that does not require an overnight hospital stay.
- Patients must exhibit at least one documented new HF symptom with objective evidence of clinical HF consisting of at least 2 physical examination findings or one physical examination findings and at least one laboratory criteria.
- The event requires initiation or intensification of treatment specifically for HF. Such treatment can include administration of intravenous agent (e.g., diuretic, vasodilator, vasopressor, or inotrope) or mechanical or circulatory intervention for HF, **OR** initiation of oral loop diuretic treatment, or intensification of oral maintenance loop diuretics for the diagnosis of HF, over a sustained period (i.e., initiation or doubling of

total daily dose through a period of ≥ 4 weeks), which is confirmed at a subsequent outpatient visit

6.4.2 Efficacy assessment 2

The secondary endpoints are:

- Time-to-first occurrence of CV death or HF hospitalization (days)
- Time-to-first occurrence of HF hospitalization or outpatient HF (days)
- Time-to-first occurrence of CV death, non-fatal spontaneous MI or nonfatal stroke (days)
- The cumulative number of composite events, including hospitalization due to HF, hospitalization due to non-fatal spontaneous MI, hospitalization due to non-fatal stroke and CV death. This endpoint is based on the total number of recurrent composite endpoints (count) and patient-specific follow-up time from randomization to end of study/death (days).
- Time to all-cause mortality (days)

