9.5.1 Efficacy variables

The secondary variables are defined as follows; the censoring mechanism will be the same as defined for the primary endpoint unless indicated otherwise:

- (1) Time from randomization to first occurrence of a confirmed composite of CV death or HF hospitalization
- (2) Time from randomization to first occurrence of a confirmed composite of HF hospitalization or outpatient HF (censoring will occur at the time of all-cause death)
- (3) Time from randomization to first occurrence of a confirmed composite of CV death, non-fatal spontaneous MI or non-fatal stroke
- (4) The cumulative number of composite events, including hospitalization due to HF, hospitalization due to non-fatal spontaneous MI, hospitalization due to non-fatal stroke and CV death. This endpoint is based on the total number of composite endpoints (count) and the patient-specific follow-up time from randomization to the last date the status of the patient was known (which could be the date of withdrawal from the study, the last visit prior to analysis cut off or the date of death).

(5) Time from randomization to all-cause mortality - patients without a death will be censored at the date of withdrawal from the study or the last day known to be alive (which may be established via telephone contact or the last visit prior to analysis cut off).

The secondary endpoints will be analyzed in order to compare LCZ696 vs ramipril using the ITT approach (i.e. estimation of the treatment effect under the ‘treatment policy’). Endpoints (1), (2), (3), and (5) will be analyzed using the same statistical analysis methods as specified for the primary analysis.

Secondary endpoint (4) will be analyzed using a negative binomial regression model with a Weibull baseline intensity function to allow flexibility if the baseline intensity is non-constant (Lawless, 1987). Treatment, STEMI/NSTEMI, PCI use at baseline and region will be included in the model as fixed effects. The relative rate ratio will be presented for LCZ696 vs ramipril together with 2-sided 95% confidence interval and 1-sided p-value.

Supportive analysis

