2.6.2 Statistical hypothesis, model, and method of analysis

The secondary endpoints will be analyzed in order to compare LCZ696 vs ramipril using the ITT approach (i.e. estimation of the treatment effect under the ‘treatment policy’).

Analysis of time to event variables

The time to event endpoints (1), (2), (3), (5) will be analyzed using the same statistical analysis methods as specified for the primary analysis. Treatment groups will be descriptively compared by presenting number and percentage of patients with events while inferential comparisons between treatment groups will be provided based on estimated hazard ratio and 95% CI. Both 1-sided and 2-sided p-values will be reported for treatment group comparison (LCZ696 vs. ramipril). Kaplan-Meier estimates of event rates will be tabulated for specific time points and will also be presented graphically.

Analysis of count variable

Secondary endpoint (4) will be analyzed using a negative binomial regression model with a Weibull baseline intensity function to allow flexibility if the baseline intensity is non-constant (Lawless, 1987). The regression model will consider the number of composite events as dependent variable with randomized treatment, STEMI/NSTEMI, PCI use at baseline and region as factors having fixed effects. Every event jump time, including the terminal event time, will be used to estimate the parameters specified in this model. For treatment group comparison LCZ696 vs ramipril, the relative rate ratio will be presented together with 2-sided 95% confidence interval and 1-sided and 2-sided p-values from the fitted model.

For descriptive summary, unadjusted annualized incidence rate will be provided along with the model-based estimates and their 95% confidence intervals will be presented by treatment groups. Also, adjusted event rate functions over time will be graphically presented from the estimated Weibull intensity.

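### The SAP 2.6.1 censoring rule for endpoint (4), read literally, closes the observation window before deaths that follow the last recorded visit, against SAP 2.6.2 and the protocol

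*SAP*

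**What the plan says.** SAP 2.6.1 defines endpoint (4) as "The cumulative number of composite events, including hospitalizations due to HF, hospitalizations due to non-fatal spontaneous MI, hospitalizations due to non-fatal stroke and CV death". For its observation period, the same section states: "For a time-to-recurrent event endpoint, the censoring date is defined as one of the following (whichever occurred first"), followed by four dates: consent withdrawal, last visit, death and analysis cut-off. The second reads "Date of the patient's last visit (including telephone visit"). The rule is then applied explicitly: "Event generating process for endpoint (4) will be censored following the censoring mechanism for a recurrent time-to-event endpoint".

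SAP 2.6.2, on the negative binomial model with Weibull baseline intensity, says: "Every event jump time, including the terminal event time, will be used to estimate the parameters specified in this model".

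Protocol 9.5.1 bases the endpoint on "patient-specific follow-up time from randomization to the last date the status of the patient was known", and names the date of death as one of the dates this could be. It has no earliest-of clause. Protocol 6.4.2 puts it as "patient-specific follow-up time from randomization to end of study/death (days").

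SAP 2.6.3 places endpoint (4) fifth and last in the hierarchy. SAP Section 4 declares no change to the protocol-specified analyses.

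**The concern.** The protocol ends follow-up at the last date on which something was known about the patient; the SAP ends it at the first of several dates. When a patient dies some time after the last recorded visit, the two rules give different windows, and under the SAP rule the death is outside.

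For a time-to-first endpoint the same kind of list does no harm, because SAP 2.5.1 censors only patients without an event. A recurrent-event analysis has no such shelter: every patient needs an end-of-observation date, whether or not events occurred, because that date sets both the exposure time and which events count.

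At stake is what a confirmatory endpoint measures. If the window is respected, CV deaths after the last visit are not counted and the rate ratio rests mainly on hospitalizations. If the deaths are kept under SAP 2.6.2 but exposure still stops at the last visit, those event times fall beyond the at-risk period and the likelihood contribution is not properly defined. Two programmers could follow the text in good faith and produce different counts for the same test.

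**Working it through.** **1. The rules applied to example patients** (no earlier consent withdrawal, all dates before cut-off)

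| Patient | SAP 2.6.1, literal | Protocol 9.5.1 |
|---|---|---|
| A: last visit month 8, CV death month 10 | 0 events in 8 months | 1 event in 10 months |
| B: HF hospitalization month 5, last visit month 8, CV death month 11 | 1 event in 8 months | 2 events in 11 months |
| C: alive at the end-of-study visit | same | same |

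Under SAP 2.6.2 the deaths of A and B should enter the model at months 10 and 11, which SAP 2.6.1 places outside follow-up.

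**2. How many events are exposed to the conflict**

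The inputs are 708 planned first primary events (SAP 3.2), 566 expected first HF hospitalization or outpatient HF events, and a pooled endpoint (4) rate of 0.192 per year (both SAP Table 3-6). There are 5,650 patients with a mean follow-up of 19 months (SAP 1.1).

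- Primary events that are CV deaths with no earlier HF event: 708 − 566 = 142. CV deaths after an HF event add to this; the documents do not give their number.
- Expected endpoint (4) events: 0.192 × 5,650 × 19/12 ≈ 1,718.
- Share: 142 / 1,718 = 8.3%.

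The matching loss of exposure is small. After month 4, visits are four months apart. Even if each of the 142 patients lost a full interval, that is 142 × 4/12 ≈ 47 patient-years out of 5,650 × 19/12 ≈ 8,946, or 0.5%. Almost all of the loss is in the event count.

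**3. Effect on power**

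The inputs, from SAP Table 3-6 and its text, are rate ratio 0.83, over-dispersion k = 6, 1-sided alpha 0.025 and 2,825 patients per arm.

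- Control rate: 0.192 × 2/1.83 = 0.2098. LCZ696 rate: 0.2098 × 0.83 = 0.1742.
- Variance of the log rate ratio: [1/(0.2098 t) + 6]/2,825 + [1/(0.1742 t) + 6]/2,825.
- Power: Φ(|ln 0.83| / √variance − 1.960).

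At t = 1 year the variance is 0.00797 and power is Φ(0.1863/0.0893 − 1.960) = 55.1%, which reproduces the stated figure. The documents do not state a one-year exposure; it is inferred from the match. At 19 months the same formula gives 63.1%.

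Removing events in equal proportion from both arms, with the rate ratio held at 0.83:

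| Exposure | Expected events | None lost | 142 lost | 300 lost (assumed total) |
|---|---|---|---|---|
| 12 months | 1,085 | 55.1% | 52.3% | 48.5% |
| 19 months | 1,718 | 63.1% | 61.7% | 60.0% |

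The 142 is a count over the full planned follow-up, so setting it against 12 months of events overstates the share lost (13.1%). The 19-month row is the consistent one.

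**The case against.** The strongest answer is that the SAP as a whole plainly means to count CV death. The endpoint definition includes it, the hierarchy repeats it, and SAP 2.6.2 says the terminal event time is used. SAP Section 4 declares no departure from the protocol, and the amendment history describes the censoring edit as adding structure for clarity. A literal reading also proves too much elsewhere: endpoint (5), all-cause death, is censored at the earliest of dates that include the last known alive date, and nobody concludes that deaths vanish from the mortality analysis.

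Much of this stands. A reader might infer that every CV death drops out of endpoint (4) because a death always follows the last visit. The documents do not support that. A visit can fall on the day of death, telephone visits count, and Protocol Section 6 allows endpoint information to be obtained from an informant. SAP 2.6.2 also argues against exclusion.

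It does not dispose of the conflict. Endpoint (5) is protected by the convention that a patient with the event is not censored; endpoint (4) sets an end date for every patient. Listing death among the four dates shows that death was meant to end follow-up, but taking the earliest date defeats this for anyone who dies after the last visit. SAP 2.6.2 makes the two sections incompatible without saying which governs. The initial SAP version, in its own 2.6.1, still carried the protocol's wording, which supports reading the current rule as an unintended change.

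The harm to the likelihood is conditional: it arises only if deaths are kept while exposure is truncated, and no text instructs that combination.

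**Conclusion.** The point holds as a contradiction in a stated rule. SAP 2.6.1, read literally, ends endpoint (4) follow-up before the death of any patient who dies after the last recorded visit. That conflicts with SAP 2.6.2 and with Protocol 9.5.1 and 6.4.2.

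At least about 142 CV deaths are potentially affected, about 8% of expected events at 19 months. This rests on the planned event counts and on those deaths falling after the last recorded visit. The power cost of losing 142 events is modest: about 3 points at one year of exposure and about 1.4 points at 19 months. It would be larger if total CV deaths were well above 142, a figure the documents do not give.

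The more important consequence is for interpretation. If the effect on CV death differed from the effect on hospitalizations, the rate ratio would largely miss it. If the two effects were the same, the ratio would be little changed. The documents do not allow the size or direction of any such shift to be stated.

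**What to change.** In SAP 2.6.1, replace the recurrent-event rule for endpoint (4) with text to this effect:

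- For patients who die on or before the analysis cut-off without earlier consent withdrawal, follow-up ends on the date of death, and a CV death on that date is counted.
- For all other patients, follow-up ends at the earliest of consent withdrawal, last visit and analysis cut-off.
- The same end date is used for exposure time and for counting events.

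This restores the protocol rule and makes 2.6.1 agree with 2.6.2. It costs one short SAP edit before database lock and a small change to the derivation program; no new data are needed.

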2.6.2 Statistical hypothesis, model, and method of analysis

The secondary endpoints will be analyzed in order to compare LCZ696 vs ramipril using the ITT approach (i.e. estimation of the treatment effect under the ‘treatment policy’).

Analysis of time to event variables

The time to event endpoints (1), (2), (3), (5) will be analyzed using the same statistical analysis methods as specified for the primary analysis. Treatment groups will be descriptively compared by presenting number and percentage of patients with events while inferential comparisons between treatment groups will be provided based on estimated hazard ratio and 95% CI. Both 1-sided and 2-sided p-values will be reported for treatment group comparison (LCZ696 vs. ramipril). Kaplan-Meier estimates of event rates will be tabulated for specific time points and will also be presented graphically.

Analysis of count variable

Secondary endpoint (4) will be analyzed using a negative binomial regression model with a Weibull baseline intensity function to allow flexibility if the baseline intensity is non-constant (Lawless, 1987). The regression model will consider the number of composite events as dependent variable with randomized treatment, STEMI/NSTEMI, PCI use at baseline and region as factors having fixed effects. Every event jump time, including the terminal event time, will be used to estimate the parameters specified in this model. For treatment group comparison LCZ696 vs ramipril, the relative rate ratio will be presented together with 2-sided 95% confidence interval and 1-sided and 2-sided p-values from the fitted model.

For descriptive summary, unadjusted annualized incidence rate will be provided along with the model-based estimates and their 95% confidence intervals will be presented by treatment groups. Also, adjusted event rate functions over time will be graphically presented from the estimated Weibull intensity.

2.6.3 Control of familywise type I error rate

The primary endpoint and the first four secondary efficacy endpoints will be included in a statistical testing strategy to control the familywise type I error rate at the 1-sided 2.5% level (in the strong sense). A hierarchical testing procedure will be employed whereby the primary hypothesis will be tested first, if rejected then the hypothesis associated with the first secondary endpoint will be tested and so on. The order of testing of the composite endpoints will be as follows:

1. Primary endpoint
2. Time to first CV death or HF hospitalization
3. Time to first HF hospitalization or outpatient HF
4. Time to first CV death, non-fatal spontaneous MI or non-fatal stroke
5. The total number of composite events (hospitalizations (including CV death) due to HF, non-fatal spontaneous MI or non-fatal stroke and CV death).

Note: Time to CV death, time to first HF hospitalization, and time to first outpatient HF (as components of the primary composite endpoint) will not be part of the above-mentioned hierarchical testing procedure.

2.6.4 Handling of missing values/censoring/discontinuations

For each patient, the information on secondary endpoints censoring will be censored as defined earlier. The primary analysis methods are valid under the assumption that the censoring mechanism is independent of the event generating process (non-informative censoring).

Sensitivity analyses have been proposed to assess robustness of the results to the potential violation of this assumption, wherever applicable.

2.6.5 Supportive analysis and sensitivity analysis

Supportive analysis

It is recognized that at the time of the first onset of symptomatic HF event some patients may discontinue randomized treatment and may be prescribed an alternative treatment for HF which could be locally available Entresto™ (sacubitril/valsartan, LCZ696). For the pre-specified secondary endpoints (1), (3) and (5) (numbering refers to Section 2.6.1), the analysis described in [Section 2.6.2](#) will estimate the treatment effect of LCZ696 vs ramipril including any effect of prescribed Entresto™ for ramipril patients who discontinued study drug and took Entresto™ as an alternative treatment. Hence, the following supportive analyses aim to estimate the pure treatment effect as though in a situation whereby Entresto™ was not an available treatment option for HFrEF. In this regard, as a sensitivity analysis, inverse probability of censoring weighted (IPCW) Cox proportional hazards model ([Robins and Finkelstein 2000](#)) will be performed on the secondary endpoints (1), (3) and (5).

Inverse probability of censoring weighted (IPCW) Cox proportional hazards model

In the IPCW analysis, the following censoring mechanism will be used for the event generating process for secondary endpoints:

- For patients randomized to LCZ696 and patients randomized to ramipril but did not take open label Entresto upon diagnosis of HFrEF event will be censored according to the mechanism described for the secondary endpoints.
- For patients randomized to ramipril who subsequently start taking open label Entresto, (defined as treatment switch), censoring will occur at the minimum of the last date the endpoint status was known, the time of death from non-CV causes, 28 days after study treatment discontinuation or start of open-label Entresto.

To adjust for the potential informative censoring, patients in the ramipril arm with event times censored due to treatment switch will be dynamically replaced in the patient risk-set by remaining uncensored patients in the ramipril arm with a matching prognostic profile by up-weighting such patients in the analysis set. At a specific time, patients in the ramipril arm who have not switched to taking open label Entresto will be assigned a weight inversely proportional to the probability of not switching till that time (i.e., patients who do not switch, but have covariates implying a high probability of switching, get a larger weight in the analysis).

Estimating IPC weights

In order to predict these patient specific time-varying probabilities, the time scale is split into small intervals based on the visit schedules. In each interval the conditional probability of being switched given patient has not switched at any earlier interval is modelled using a logistic regression model with the following covariates–

- **Time independent (baseline) covariates:**

Age (in years), baseline LVEF, baseline eGFR (ml/min/1.73m²), history of prior MI (yes/no), history of diabetes (yes/ no), Atrial Fibrillation associated with qualifying MI (yes/no), baseline Killip class, use of PCI for qualifying MI (yes/ no), use of ACEI/ARB in last 24 hours prior to randomization (yes/ no), use of IV treatment for qualifying MI (yes/ no)

- **Time dependent covariates:**

Systolic BP (mmHg), Heart rate (bpm), eGFR (ml/min/1.73m²), *use of PCI or CABG (yes/ no), *use of ICD/CRT (yes / no)

*(*procedures related to any post-randomization MI event)*

Predicted probability of switching at a specific time for a patient will be obtained by multiplying individual conditional probabilities of switching in intervals prior to that time point. To minimize impact of extreme weights (e.g. patients not switched though having very high estimated probability to switch), the stabilized version of weights will be used which is defined as the ratio of predicted probabilities of not being switched by time t –

- from the logistic regression with only baseline covariates
- from the logistic regression with both baseline and post-baseline covariates

It is conceivable that the above logistic regression procedure of estimating weights may not converge due to reasons including (but not limited to) sparseness of switchers in the subpopulations implied by the selected covariates resulting into an infinite likelihood due to complete or quasi-complete separation or numerical difficulties in evaluating an overly complex likelihood function. Should such problems arise, the logistic regression model used to determine the IPC weights will be simplified by pooling pre-specified time intervals (thereby extending the time windows in which time-dependent covariates are assessed). If that still does not solve convergence problems, the model will be simplified by removing covariates.

All patients randomized to LCZ696 will be assigned a weight of 1 for all time intervals.

Estimation of treatment effect

Following the estimation of weights, a weighted Cox proportional hazard model will be fitted to the time to event endpoints (1), (3) and (5). The model will be stratified by STEMI/NSTEMI while treatment, region, PCI use at baseline will be included as fixed effects factors. The hazard ratio for LCZ696 vs. ramipril, the associated 2-sided 95% confidence interval and the 1-sided and 2-sided p-values will be presented from the analysis.

On-treatment analysis

Endpoint (4), the total number of confirmed hospitalizations for HF, MI and stroke (including CV death) will be redefined for the patients who are prescribed open label Entresto™ as the

total number of composite endpoints from randomization up to 28 days after the time of study treatment discontinuation. The analysis methods will remain the same as specified above.

Sensitivity analysis

If the study is stopped early for efficacy at the second interim analysis, or the study is terminated early by the sponsor due to prolonged COVID-19 impact, a sensitivity analysis using the primary/main analysis model as specified in [Section 2.6.2](#) will be performed for each secondary endpoint, including all data accrued up to the end-of-study analysis cut-off.

If the study is not stopped at the second interim analysis and continues to the end, a sensitivity analysis using the primary/main analysis model as specified in [Section 2.6.2](#) will be performed for each secondary endpoint, including data accrued prior to 01-Mar-2020.

